OCPs increase the risk of MetS specifically by producing an atherogenic lipoprotein phenotype, increasing blood pressure and/ or body weight while metformin modestly decreases MetS risk by decreasing body weight and improving lipid phenotype. The combination of OCP and metformin (OCP, through lowering androgens, and metformin, through improvement in insulin sensitivity) will likely decrease the prevalence of MetS, thereby altering the risk profile for the development of diabetes and possible cardiovascular disease (CVD) in young women with PCOS.

Patient Population

The population will consist of 240 overweigh/obese women with hyperandrogenic PCOS, age 18-40 years old. Subjects must have a body mass index (BMI) between 25-48 kg/m². Subjects will be diagnosed with PCOS defined by the Rotterdam criteria.

Study Design

This will be a three-arm, double-blind, double-dummy, multicenter, prospective, randomized clinical trial comparing OCP + placebo vs. Metformin + placebo vs. OCP + Metformin on the prevalence of MetS in women with PCOS. This 6-month study will consist of a screening visit, followed by 5 study visits. No longer term follow-up is planned.

Treatment

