Once potential women have been prescreened, they will be referred to the site clinical coordinator or his/her designee for a screening visit. The consent process will be conducted according to each site's standard operating procedures.

Inclusion and exclusion criteria will be reviewed. After the study has been completely explained to the woman, she will be given the informed consent documents to review. Some individuals may wish to complete the informed consent process at the time of this discussion. In these cases, the informed consent documents will be signed once all questions are resolved. In other cases, the subjects may wish to take the consent forms home for further consideration. In these cases, the coordinator will confirm the woman's willingness to be contacted, and set up a tentative timeframe to be back in touch with the subjects. The consent can be signed once all questions have been answered to the satisfaction of the potential subject. A signed informed consent document, approved by the central IRB, will be confirmed on all subjects prior to the baseline evaluation.

In order to be eligible for enrollment and randomization, the woman must be confirmed to meet all inclusion and exclusion criteria described above.

Intervention Group Assignment

After screening is completed the information will be uploaded in RedCAP electronically, and randomization will be performed by IDS at the time of the randomization visit. Subjects and study coordinators will not be informed of their treatment assignment.

Study Interventions

Interventions, Administration and Duration

Study Medication: All subjects will be randomized to receive either OCP + placebo, Metformin + placebo or OCP + Metformin for 24 weeks. All medications will be self-administered. Once eligibility has been confirmed and subjects have been randomized, the site staff will distribute appropriate medications during each visit. The subject will receive enough pills to last until the next visit (additional pills for each arm will be distributed at the start of the study for situations if/when the visit window must be utilized; subjects will receive appropriate instructions regarding the extra medication). Subjects will be required to wash out of any excluded medications prior to enrollment in the study.

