7.2.10 Week 25 patient contact

This contact will be made one week after patient has completed taking the medication to review any side effects and answer any patient questions. This patient contact will close out the study adverse events.

Study Risk and Benefits

Risk

The risks of these studies include the risks of the study procedures, and the risk of the study interventions. These will be discussed separately below.

Risks of Study Procedures

These risks include the risk of phlebotomy, oral glucose tolerance test and DXA. The risks of phlebotomy include pain at the phlebotomy site, bruising and rarely bleeding, and potentially iatrogenic anemia. Risks of the oral glucose tolerance test include the risks of multiple phlebotomy or in some cases the risk of insertion of an IV. The risks of IV insertion include the risks of phlebotomy, and additionally the induction of anemia, and infection at the site. Glucose ingestion can cause nausea and in rare instances vomiting upon ingestion. We have never experienced an allergic reaction to the oral glucose solution, though this is possible. Some subjects also may experience an episode of hypoglycemia after the test which can present with increased heart rate and anxiety. In the most severe cases, fainting can occur. The DXA scan will involve exposure to radiation, on average 2-3 milliroentgens of radiation during the procedure. The average amount of radiation that a person would receive from a DXA scan is less than 1% of the background radiation experienced from living in the Philadelphia area for one year, for example.

Risks of Study Interventions

Oral Contraceptive Pill - OCP used in this study is low dose (20micrograms ethinyl estradiol), which may cause bloating, nausea, breast tenderness, mood changes, weight change and headaches. Common side effects include breakthrough bleeding and amenorrhea. OCP are also associated with increased risk for cardiovascular disease, especially venous thromboembolism and stroke. OCP can also cause hypertension and alter blood lipid and glucose levels. Interactions with drugs such as phenobarbital, phenytoin, and rifampin increase the metabolism of oral contraceptives, thus decreasing the effectiveness as a method of birth control. Table lists all side effects recorded in women in the OCP arm of the recently completed OWL-PCOS study (n=49). Roughly same numbers are expected in this current study.

OWL-PCOS study	Number of		Number of

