- 1. Both MetS and PCOS are major health problems and the risks of common treatments (OCP or metformin) on development of MetS are poorly understood.
- 2. Knowledge gained from this investigation will identify optimal strategies for treatment of overweight/obese women with PCOS
- 3. Understanding the underlying pathophysiology for alterations in metabolic risk with OCP or metformin use, will provide important information for future studies.

Statistical Considerations

General Design Issues

This will be a randomized, double-blind, double dummy clinical trial of three types of medication, OCP + placebo, metformin + placebo or OCP + metformin. We will track all subjects to completion. Subjects will be randomized 1:1:1 to the three treatments.

Randomization

Randomization is a critical feature of a clinical trial because it prevents treatment-selection biases. The study statistician will develop the programs for the randomization; however, the final random seeds used to generate the randomization scheme will be prepared by a statistician in PSU's Department of Public Health Sciences independent of the study in order to keep the study statistician blinded as well. The randomization scheme for this study will use variable-size, random permuted blocks to ensure that the number of participants in each treatment arm is balanced after each set of *B* randomized participants, where *B* is the block size. Furthermore, the randomization will be stratified by recruitment site (UPenn/PSU), race (AA/non-AA), and the presence of MetS at baseline (yes/no). Randomization to the metformin or OCP arms will use 1:1:1 allocation.

Outcomes

Primary Outcome Measurements

The primary outcome for this trial is prevalence of MetS.

Secondary Outcome Measurements

We may assess change in HDL-C function, serum apolipoproteins, lipid particle size and number, body fat distribution, BMI, serum adipokines, HbA1c, glucose and insulin sensitivity, serum markers of inflammation, free fatty acids, androgens, quality of life parameters, cognitive testing and predictive factors for change in prevalence on MetS

Sample Size and Accruals

Sample Size and Power Calculations

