All serious adverse events (SAEs) that occur from randomization through thirty days after the last dose of study medication must be reported. A serious adverse event is defined as: fatal or immediately life-threatening; severely or permanently disabling; requiring or prolonging inpatient hospitalization; overdose (intentional or accidental); ; or, any event adversely affecting the study's risk/benefit ratio. Additionally, any event that, based on appropriate medical judgment, may jeopardize the subject's health and may require medical or surgical intervention to prevent one of the outcomes listed above is considered an SAE.

If an SAE occurs and is thought to be related to the study medication, the study medication will be discontinued.

The site PI will report the SAE by completing and signing the Serious Adverse Event Report Form Subjects will be identified by subject identification number only. No other identifying information will be included on the form.

The site PI must determine and record on the SAE form whether the SAE is unanticipated or anticipated, and if it is related, possibly related, or unrelated to participation in the research.

The DSMB and FDA (as applicable) will be notified and provide a determination regarding the SAE.

These determinations will dictate timeframes for sites' submission to the DSMB (Table 12):

ТҮРЕ	SITE		
Unanticipated and related/possibly	Report to DSMB within 1 business		
related SAE, fatal or life-	day of discovery		
threatening			
Other unanticipated and	Report to DSMB within 1 business		
related/possibly related SAE	day of discovery		
Anticipated and related/possibly	Report to DSMB within 5 business		
related SAE	days of discovery		
Unrelated SAE (anticipated or	Report to DSMB within 10 business		
unanticipated	days (no more than 3 weeks) of		
	discovery		

Upon receiving notification of an SAE, the DSMB will review it via a closed-session email or conference-call discussion.

The PI will evaluate the frequency and severity of the SAEs and determine if modifications to the protocol and consent form are required. Site PIs will report the SAE to their site IRB according to local IRB requirements.

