Adverse events deemed non-serious will also be recorded throughout study participation from the start of study drug through one week after the last dose of study medication. If an anticipated serious adverse event occurs at a frequency greater than expected, the DSMB will be notify the PI by the end of the next business day of discovery and follow the procedures for reporting serious and unanticipated and related adverse events. If an adverse event not initially determined to be reportable to the FDA under 21CFR312.32 is so reportable, the PI will report the adverse event to the FDA within 15 calendar days after the determination is made.

Data Monitoring

There will be no pre-determined stopping rules and no interim analysis.

Study Monitoring

A monitoring plan that satisfies the ICH/GCP guidelines for clinical monitoring will be used. The Penn designated monitor at the Women's Health Clinical Research Center, will lead this effort, and report findings to the PI of both sites and the DSMB when necessary. The Penn designated monitor will have full knowledge of the study protocol, Manuals of Procedures, and is familiar with the database system redcap and is trained to review patient charts. The Penn designated monitor along with the Project Manager/Lead Study Coordinator at each site will be responsible for training and supervising other personnel.

Once personnel at participating site are trained to recruit patients, the Penn designated monitor will be sent to the site to help initiate the study according to the study protocol, and to ensure that the clinical site meets the scientific, clinical, and regulatory requirements. For example, the Penn designated monitor will review all signed and dated forms (such as financial disclosure forms), the curriculum vitae and certifications of the investigators and personnel, CRF training, and the written IRB approval of the protocol and consent form.

The Penn designated monitor will return to the clinical site after a defined number of patients are recruited (recruitment of the first 5 patients) and yearly thereafter.

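### SAEs must be reported to 30 days after the last dose, but scheduled contact ends, and adverse events are closed out, at 7 days, leaving 23 days with no scheduled enquiry

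*Combined protocol and SAP*

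**What the plan says.** The protocol sets two safety windows that end at different times.

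- **Serious events.** The part headed Serious Adverse Events, within Adverse Event Reporting, gives this rule: "All serious adverse events (SAEs) that occur from randomization through thirty days after the last dose of study medication must be reported".
- **Non-serious events** (same section, after the DSMB timelines): recorded "from the start of study drug through one week after the last dose of study medication".

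The final contact is described in section 7.2.10: "This contact will be made one week after patient has completed taking the medication", followed by "This patient contact will close out the study adverse events". No exception is made for serious events. In Table 6 the end-of-study contact is the last column and the last point at which adverse events are reviewed. In Table 9 the week-25 contact is the last row. The Study Design paragraph of the Synopsis adds: "No longer term follow-up is planned".

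Treatment is described in Interventions, Administration and Duration as ending in "OCP + Metformin for 24 weeks" for the combination arm, with the same duration for the other two. General Design Issues says "We will track all subjects to completion", without saying how the post-dose SAE window is covered for a woman who stops medication early. Section 7.2.9 offers an early termination visit only after at least 12 weeks on study medication.

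**The concern.** The close-out at one week matches the non-serious window exactly and the SAE window not at all. The protocol sets two windows but schedules a final contact for only the shorter one. A site that follows Tables 6 and 9 to the letter closes adverse events on day 7 and does not ask again, although serious events remain reportable for a further 23 days.

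What is at stake is completeness of the serious safety data. Adverse events are reviewed at every scheduled contact after randomization, and this stops at week 25. The DSMB reporting timelines in Table 12 all run from discovery, so an event that nobody asks about starts no clock. The SAE definition includes hospitalization and life-threatening events, and Risks of Study Interventions states: "OCP are also associated with increased risk for cardiovascular disease, especially venous thromboembolism and stroke". A woman admitted to another hospital after her close-out contact would have to tell the study team unprompted.

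**Working it through.** This is calendar arithmetic; no power or error-rate formula applies.

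**Inputs**
- Treatment length: 24 weeks (Interventions, Administration and Duration).
- Last contact: week 25, ordinary window weeks 24 to 26, outer limits weeks 23 and 27 (Table 9).
- SAE window: to day 30 after the last dose (Serious Adverse Events).
- Non-serious window: to day 7 after the last dose (same section).

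**Step 1: reproduce the plan's own interval.** Week 25 − week 24 = 1 week = 7 days. This agrees with the one week in section 7.2.10 and with the non-serious window.

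**Step 2: nominal gap.** 30 − 7 = 23 days, that is days 8 to 30 after the last dose. As a share of the post-dose period, 23/30 = 76.7%.

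**Step 3: share of the whole SAE window.** Taking dosing to start at randomization and run for the full course, 24 × 7 = 168 days, and 168 + 30 = 198 days. 23/198 = 11.6%.

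**Step 4: do the visit windows close the gap?** Day 30 after a week-24 last dose falls at week 24 + 30/7 = 28.3, beyond the week-27 outer limit. Days left uncovered = 30 − 7 × (contact week − last-dose week), with a minimum of 0:

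| Last dose | Contact wk 24 | Contact wk 25 | Contact wk 26 | Contact wk 27 |
|---|---|---|---|---|
| Week 22 | 16 | 9 | 2 | 0 |
| Week 23 | 23 | 16 | 9 | 2 |
| Week 24 | 30 | 23 | 16 | 9 |
| Week 25 | – | 30 | 23 | 16 |

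Of these combinations, only a last dose at week 22 with a contact at the week-27 limit covers the full 30 days. That combination does not fit section 7.2.10, which ties the contact to one week after the last dose. Under that section the gap is 23 days whatever the date of the last dose. Table 9 counts from the start of the study and section 7.2.10 from the end of medication, so the two can give different dates for the same contact.

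**Step 5: women who stop early.** A woman who stops medication but stays on the visit schedule could have later contacts covering some or all of her 30 days. A woman who leaves before 12 weeks of medication has no early termination visit. The documents do not settle how either is followed for serious events.

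**The case against.** The best case for the plan is that nothing here is contradictory. One passage sets a duty to report and the other sets a contact date; a reporting window can outlast scheduled contact, and a site that learns of an SAE on day 20 must still report it. Since non-serious recording ends on the day of the week-25 contact, the close-out sentence most naturally refers to routine events. Women are counselled on warning signs (section 8.2.1), and same-day access to an investigator is described under Protection Against Risks. The manual of procedures, to which the protocol often defers, could contain a day-30 check. The percentages count days rather than expected events, and the protocol reports no serious adverse events among 49 women given a low-dose OCP in OWL-PCOS.

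Much of this stands. It is a gap in ascertainment, not a removal of the duty to report, and the number of events that would be missed cannot be estimated from the documents. The Synopsis statement on follow-up is weak support, because it describes the general study plan rather than SAE capture.

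It does not remove the gap. Reading the close-out as applying only to non-serious events explains the sentence but supplies no later SAE enquiry, and the protocol lists none. Counselling and access help a woman who chooses to call; neither is a scheduled question, and neither is stated to extend past the last dose. A day-30 check in the manual would still conflict with an unqualified close-out in the protocol. Zero events in 49 women does not exclude a real risk: the one-sided 95% upper limit is 1 − 0.05^(1/49) = 5.9%. That figure also comes from a 16-week trial and does not address the period after dosing.

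**Conclusion.** The concern holds. On the nominal schedule, 23 of the 30 post-dose days that the protocol makes reportable have no scheduled enquiry. With a last dose at week 24, the Table 9 limits move this between 9 and 30 days but never to zero. SAE capture over those days is passive as the protocol is written, so following it can give incomplete serious safety data.

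This rests on three assumptions: a full 24-week course, a final contact at the nominal time, and no day-30 check in the manual of procedures. The conclusion is firm for the protocol text and less certain for what sites do in practice. The MetS analysis is unaffected. The change should be made because it is cheap and improves safety ascertainment; the finding does not threaten the trial's main result.

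**What to change.** Reconcile section 7.2.10, Tables 6 and 9, and the serious and non-serious windows in the Adverse Event Reporting section:

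1. Keep the week-25 contact, and state that it closes out non-serious adverse events only.
2. Add one brief SAE-only contact, by the participant's preferred method, at or after the end of the stated SAE window.
3. Count that contact from the actual date of the last dose, and say that it applies also to women who stop medication early, including before 12 weeks.
4. Add the contact to Tables 6 and 9, with a window that does not open before day 30.
5. State whether the week-25 contact is dated from the start of the study or from the last dose.

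An explicit instruction at week 25 to report later serious events would be a useful addition, but alone it would leave capture passive.

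The cost is a wording amendment and one short remote contact per participant, at most 240 in all, using a method already in place. Each participant's close-out moves 23 days later (30 − 7). No treatment or clinical rule changes.

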The intervention will consist of randomizing subjects to one of three arms. Subjects will either be assigned to OCP + Placebo, Metformin + Placebo or OCP + Metformin. Metformin will be initiated in a step-up fashion using extended release pills as they are associated with fewer gastrointestinal side effects. Subjects will begin with one tablet of metformin every night for 5 days, eventually building up to 4 tablets every night, with the maximum dose of metformin being 2000 mg. In regards to OCP, previous randomized clinical trials (RCTs) have shown that 20mcg ethinyl estradiol/norethindrone 1.0 mg was well tolerated. The study will utilize a 20mcg OCP but a less androgenic third generation progestin (desogestrel 0.15mg) with potentially lesser impact on lipids and insulin sensitivity. All subjects with no menses the 3 months prior to screening will be given medroxyprogesterone acetate, at the screening visit, after a negative pregnancy test (in order to induce menses). Placebo pills will be administered to individuals randomized to OCP or metformin only in order to maintain study blinding. Subjects will undergo 6 in person study visits and life style modification counseling regarding diet and exercise. Patient contact will be made via the subject's preferred contact method after randomization and at the end of each month when there is no in person visit to ensure study compliance with medications, keeping study logs and to review side effects.

Primary efficacy parameter

Determine the prevalence of MetS after randomizing to OCP, metformin or OCP+metformin for 6 months. MetS will be defined by NCEP ATPIII criteria as the presence of at least 3 of the following 5 criteria: TG≥150mg/dl, HDL-C<50mg/dl, BP≥130/≥85mmHg, WC>88cm and fasting glucose≥100mg/dl.

Secondary/Tertiary efficacy parameters

Assess change in HDL-C function, serum apolipoproteins, lipid particle size and number, body fat distribution, BMI, serum adipokines, HbA1c, glucose and insulin sensitivity, serum markers of inflammation, free fatty acids, androgens, quality of life parameters, cognitive testing and predictive factors for change in prevalence on MetS.

Subjects will have the option to consent to storage of their blood for future additional analysis as related to the disease of interest. No research/future analysis will take place, prior to gaining IRB approval.

Statistical Analysis

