 - Determine need for medroxyprogesterone acetate (if subject has had no menses in the last 3 months)
 - * Remote option for completion, utilization of this option at PI discretion
 - 4. Perform urine pregnancy test.
 - 5. Record vital signs and biometrics
 - 6. Blood draw for both screening labs (as needed) and safety labs (as needed)
 - Review Hirsutism (F-G) Score
 * Remote option for completion, utilization of this option at PI discretion
 - 8. Transvaginal Ultrasound (if indicated)
 - 9. Review electronic Medical Record (if available)
 - If subjects are patients through the University of Pennsylvania Health System or Hershey Medical Center, electronic medical records will be reviewed to verify eligibility. Screening blood laboratory tests that were completed within the last year can be substituted for laboratory tests collected at screening and randomization visit.

Table 7: Screening Blood Tests

Category	Tests		
Safety Labs**	Complete metabolic panel, lipid profile		
Screening Labs	TSH*, Prolactin*, HbA1c*, CBC*, 17OH Progesterone^, DHEAS^,		
	Total Testosterone [#] ,		

*If drawn within 1 year of screening, eligible for use to determine eligibility criteria.

^ If drawn within lifetime prior to screening, eligible for use to determine eligibility criteria.

If FG≥6 (≥2 for women of Asian descent) do not need to draw lab. Eligibility criteria can be determined without this lab value.

** If drawn within 2 months of screening, eligible for use to determine eligibility criteria. These safety labs must be drawn at Randomization visit if not drawn at Screening visit.

7.2.2 Randomization Visit:

- 1. Review menstrual history
- 2. Complete urine pregnancy test
- 3. Record vital signs and biometrics
- 4. Complete fasting blood draw and Safety labs (as needed)
- 5. Optional whole blood draw for DNA testing
- 6. Start the oral Glucose Tolerance Test (this may be first since the subjects are fasting)
- 7. Review Lifestyle Modification Counseling
- 8. Complete PCOSQ, CESD-R, STAI, FSDS-R & FSFI
- 9. Cognitive testing
- 10. Complete DXA scan
- 11. Transvaginal Ultrasound (if indicated)
- 12. Randomize into study arm
- 13. Dispense Logs/Medications
 - Review medication instructions

*For more detailed information regarding the order in which study procedures should occur, please refer to the Manual of procedures.

*Complete patient contact with subject two weeks after this visit. COMET-PCOS PROTOCOL V10.1 NOVEMBER 30, 2021

Category	Tests		

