Metformin - There is a small risk of lactic acidosis among women taking this medication. This most commonly occurs in patients with poorly controlled diabetes and impaired renal function. Women with these pre-existing medical problems will be excluded from the protocol as per the exclusion criteria. There have been reports of lactic acidosis induced by exposure to iodine-containing radiocontrast agents, such as those used for an intravenous pyelogram. Metformin XR will be stopped prior to procedures involving exposure to radiocontrast agents to reduce the chance of developing lactic acidosis (one week prior to medication and resume one week after the test). The development of lactic acidosis for any reason will be a reason for discontinuing participation in the study. Metformin XR is pregnancy category B with no known human teratogenic risk and no known embryonic lethality in humans. Metformin XR has been used throughout pregnancy in a number of studies with no adverse maternal or fetal effects. If a subject is pregnant during any part of the study, her participation will be stopped.

Preventing Pregnancy - All subjects will be asked to use barrier contraception during this study. Pregnancy tests will be performed at each in person study visit.

Menstrual irregularity - All subjects will be asked to keep detailed menstrual log and study coordinators and site Pls will review symptoms. Subjects may present with break through bleeding on the low dose OCP. Some subjects in the metformin arm may not have any menses during the study period. We will induce menses by administering medroxyprogesterone acetate at the screening visit if a subject has not had menses for 3 months. There is no data to suggest that lack of menses in the metformin arm for 6 months will increase risk of endometrial hyperplasia. In fact, several studies have described the biological plausibility of metformin having a protective effect on the endometrium. If a subject has not had menses during the study, we will administer medroxyprogesterone acetate after confirming a negative pregnancy test at the end of the study.

Potential Benefits of the Proposed Research to Human Subjects and Others

The subjects in this study will not benefit directly. The results from the study can be applied in the future to patients who stand to benefit from this information.

Importance of the Knowledge to be Gained

The importance of this study is high for the following reasons:

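### The required adverse-event windows leave out the time from consent to randomization or first dose, so events then after screening medroxyprogesterone or during the baseline glucose tolerance test need not be recorded or reported

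*Combined protocol and SAP*

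**What the plan says.** The Serious Adverse Events subsection of Adverse Event Reporting sets the first window: "All serious adverse events (SAEs) that occur from randomization through thirty days after the last dose of study medication must be reported". The same section says that non-serious events will be recorded "throughout study participation from the start of study drug through one week after the last dose of study medication". The site investigator must judge whether an SAE is related to taking part in the research, and the timetable for reports to the DSMB depends on that judgement.

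Two protocol-directed exposures are placed ahead of these dates.

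- **Screening progestin.** The Synopsis (Treatment) says: "All subjects with no menses the 3 months prior to screening will be given medroxyprogesterone acetate, at the screening visit". The menstrual-irregularity paragraph of section 8.2.1 repeats it: "We will induce menses by administering medroxyprogesterone acetate at the screening visit if a subject has not had menses for 3 months".
- **Baseline OGTT.** In section 7.2.2 (Randomization Visit), item 6 reads: "Start the oral Glucose Tolerance Test (this may be first since the subjects are fasting". Item 12 is "Randomize into study arm", and item 13 is dispensing. A footnote refers the detailed order of procedures to the manual of procedures.

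Risks of Study Procedures warns of hypoglycemia after the OGTT and adds: "In the most severe cases, fainting can occur".

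In Table 6 the adverse-event review row is empty at Screening and Randomization. Its first mark is at the patient contact after randomization.

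**The concern.** The protocol counts the risks of its procedures among the risks of the study, and its SAE form asks about relatedness to the research as a whole, not only to study medication. Yet both windows are tied to randomization or to study drug. A woman admitted to hospital after fainting at her baseline OGTT, or with a serious event on the screening progestin before she is randomized, meets the SAE definition but falls outside the reporting rule. The documents give no reason for requiring a report of the same OGTT event at week 24 and not at baseline.

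What is at stake is whether the DSMB and the IRB receive a complete account of research-related harm, including harm to women who take the progestin and are then not randomized.

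**Working it through.** There is no power or sample-size figure to reproduce. The check sets the opening of each window against the order of procedures, then against every other route by which an event could be recorded.

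**Step 1. Exposures against windows**

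| Exposure | When | SAE window (opens at randomization) | Non-serious window (opens at first dose) |
|---|---|---|---|
| Screening medroxyprogesterone | Screening visit | Not open | Not open |
| Baseline OGTT | Randomization visit, item 6, may be first | Not open in the listed order (randomization is item 12) | Not open (dispensing is item 13) |
| OGTT at week 24 or early termination | End of treatment | Open | Open |

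The windows go by when an event begins, not by what caused it. The gap is therefore limited to events that begin after consent and before randomization (serious) or before first dose (non-serious).

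**Step 2. How far this depends on the listed order.** If the manual of procedures placed randomization ahead of the OGTT, a serious OGTT event would fall inside the SAE window. Non-serious events would still fall outside unless study drug had also been started, which is implausible for a baseline test. No reordering within the randomization visit changes the position of a drug given at the screening visit.

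**Step 3. Scheduled review.** Neither the screening checklist (7.2.1) nor the randomization checklist (7.2.2) contains an adverse-event review. The checklists for weeks 4, 8, 16 and 24 all do. Table 6 agrees with the checklists, although it does schedule a concomitant-medication review at both early visits.

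**Step 4. Other routes.** The research-meetings paragraph under Protection Against Risks has coordinators pass on adverse medical events that participants report. It gives no start date, recording form or DSMB timetable. For adverse events sent to the IRB it points forward to the later section, and so back to the two windows.

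**Step 5. Scale.** Inputs: 240 women randomized and 15% drop-out (Sample Size and Power Calculations); an OGTT at randomization and at week 24, or at early termination after at least 12 weeks on medication (Table 6, section 7.2.9).

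- Baseline OGTTs: 240, one per randomized woman.
- Later OGTTs, upper bound: 240.
- Later OGTTs, lower bound, if no drop-out has one: 240 × (1 − 0.15) = 204.
- Share before both windows: 240 / (240 + 240) = 50%, up to 240 / (240 + 204) = 240 / 444 = 54%.

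Women who have the baseline OGTT and are then not randomized would add to this. The documents do not say how many women will need medroxyprogesterone. Purely as an assumption, 20% to 40% of 240 would be 48 to 96, with screen failures on top; the conclusion does not rest on that range.

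**The case against.** A reader might infer that harms from the screening progestin and from every baseline OGTT can never be captured. The documents do not support that.

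- The coordinators' relay has no start date. OGTTs are run by trained nurses with investigator back-up, so a faint during the test would be seen. The DSMB's remit in its own section is safety information generally. What is missing is a rule that requires recording and reporting, not all chance of capture.
- A progestin-related SAE that begins after randomization is reportable, and a non-serious one that begins after first dose is recorded. The same holds for delayed OGTT events.
- The statement about all baseline OGTTs rests on the listed order, and the manual of procedures was not available.
- It is tempting to add that symptoms present before the first dose cannot be told apart from treatment-emergent ones. That is too strong: a six-month medical history is taken at screening, and menstrual history, vital signs and concomitant medications are reviewed at randomization. These give a partial baseline, though none is a symptom review after the progestin.
- The risk sections list no risk for medroxyprogesterone. Consent pages were removed from the text, and section 7.2.1 requires that women be told of potential drug side effects, so no conclusion can be drawn about what women are told.
- The 50% to 54% counts tests. The protocol gives no event rate, describes vomiting as rare and ties fainting to the most severe cases.

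All of this stands and limits the point. None of it supplies a required record or DSMB report for an event that begins before the windows open.

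**Conclusion.** The gap is real but narrow. Followed as written, the protocol requires no recording and no DSMB report for events that begin between consent and randomization (serious) or first dose (non-serious). Screening medroxyprogesterone lies in that interval on the protocol's own text; the baseline OGTT lies there on the order listed in section 7.2.2. On that order, all 240 baseline OGTTs are affected. The number of harms that would go unreported cannot be estimated from the documents and is probably small.

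The matter is one of safety oversight. A reader might infer biased safety or efficacy comparisons between arms; that does not follow, because these events precede treatment. The primary analysis and power are untouched. The change is worth making because a serious research-related event can fall outside the rule and the remedy is cheap.

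**What to change.** 1. **Serious Adverse Events:** start reporting at the first protocol-directed procedure or drug after consent, including for women who are then not randomized.
2. **Non-serious events (Adverse Event Reporting):** from the same point, record events attributed to a study procedure or to screening medroxyprogesterone. Flag them as pre-treatment and keep them out of the by-arm comparison.
3. **Table 6:** mark adverse-event review at the Randomization visit and match it in the 7.2.2 checklist. Add a check for screen failures who took medroxyprogesterone, since they may never attend that visit.
4. **Reconcile** Table 6, the research-meetings paragraph and both reporting windows, so that one start date applies throughout.

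The cost is amendment wording, a mark in Table 6, a pre-treatment flag on the event form, the check on screen failures and a small number of extra records. Eligibility, treatment, sample size and the primary analysis are unchanged.
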